8.5. CLINICAL LABORATORY EVALUATIONS

Descriptive summaries of actual (absolute) values and changes from baseline values if applicable will be presented in the tables for the following by visit for the full analysis set:

- Chemistry: sodium, potassium, calcium, phosphate, chloride, total bilirubin, alkaline phosphatase, lactate dehydrogenase (LDH), aspartate aminotransferase (AST), alanine aminotransferase (ALT), gamma glutamyl transferase (GGT), albumin, total protein, creatinine, urea nitrogen, uric acid, serum iron and transferrin
- Hematology: hemoglobin, leukocytes, differential blood count of leukocytes, platelet count
- Hormone Levels: thyroid status (TSH, fT4, and fT3 levels) and morning cortisol
- Glucose Metabolism: HbA1c.
- Lipid Metabolism: Total cholesterol, triglycerides, HDL and LDL

Laboratory values will also be displayed in the data listings and those that are outside the normal range will be flagged, along with corresponding normal ranges. Any out-of-range values that are identified by the investigator as being clinically significant will be presented in a data listing.

For each laboratory parameter, if applicable, shifts in assessments of abnormality from baseline to each post-baseline visit will be presented (shift tables).

8.6. VITAL SIGNS

Descriptive summaries of actual values and changes from baseline will be calculated for Temperature, Systolic Blood Pressure (SBP), Diastolic Blood Pressure (DBP), Heart Rate (HR), and Respiratory Rate (RR). These summaries will be presented by visit.

A data listing of vital signs will also be provided.

8.7. EXPOSURE AND COMPLIANCE

Summary tables will be presented for the following variables:

- Total duration of treatment
- Total number of actual doses
- Total actual dosage (mg)
- Compliance rate

The dosage (mg) is the product of the dose volume (mL) and dose concentration (mg/mL) reported in the eCRF. When there are three or more observed consecutive doses with more than 15% difference between actual dose and expected dose (0.24mg/kg/week), it will be considered as a dose reduction/increase. The frequency and percentages of subjects for dose not changed, dose increased or decreased will also be summarized by visit.

The compliance rate will be calculated based on the rules in [Section 5.4](#). Compliance rate will be summarized using the following categorization; <80%, ≥80%, ≥90%, ≥95% and 100%.

Listings will be presented for all exposure information.

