* Banked blood samples may be used for additional characterization of anti-drug antibody responses

11) At Visit 2 only: Study drug dose adjustment, as needed

12) At Visit 2 only: Study drug & subject diary dispensing

13) At Visit 3 only: Fundoscopy (to rule out blurred disc margins)

TransCon hGH Dose:

TransCon hGH will be dosed at 0.24 mg hGH/kg/week. This dose was selected due to variable compliance with daily dosing regimens and to be consistent with the pivotal phase 3 heiGHt Trial that has been ongoing since November 2016. The initial volume of TransCon hGH administered will be calculated using the weight measurement obtained at Visit 1 and the TransCon hGH bracketed weight chart.

Dose Adjustment Parameters:

The following parameters may be used by the investigator to adjust the TransCon hGH dose without Medical Monitor pre-approval.

At Visit 2, the TransCon hGH dose may be adjusted by the investigator based on the TransCon hGH bracketed weight table.

Additionally, the goal for IGF-1 should be between 0 and + 2.0 SDS (unless a different target is identified in consultation with the Medical Monitor). Thus, if the IGF-1 SDS measured at Visit 2 (or the C_{max} Visit, as applicable) is < 0 SDS, and following confirmation of IGF-1 level as < 0 SDS by a second measurement collected 5 days post-dose (± 1 day), the dose may be increased by approximately 20% to the next higher weight bracket by the investigator.

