9.3 Treatment Administered

TransCon hGH will be provided as a lyophilized powder in single-use glass vials to be reconstituted with 1 mL sWFI. Two concentrations will be available, the less concentrated for lighter weight subjects, the more concentrated for higher weight subjects:

- 12.1 mg hGH/vial (11.0 mg hGH/mL when reconstituted)
- 24.2 mg hGH/vial (22.0 mg hGH/mL when reconstituted)

Table 1 shows the weight ranges and corresponding drug concentration and volume to be administered to all subjects, regardless of weight, with an average dose of 0.24 ± 0.02 mg hGH/kg/week. If the concentration suggested in the preferred dosing column is unavailable, alternative dosing should be followed. It is imperative that investigators **do not** calculate a weight-based dose but rather follow the chart and administer the exact volume (based on weight) of the given concentration as indicated.

TransCon hGH will be injected SC into the left and right buttock, left and right thigh, and left and right abdomen by the subject/parent/legal guardian/caregiver except at Visit 1 where the trial staff may administer the first dose. To minimize local side effects, it is recommended to rotate the 6 injection sites in a subsequent manner (eg, right thigh, right abdomen, right buttock, left thigh, left abdomen, left buttock).

Table 1
TransCon hGH Bracketed Weight Table

Weight (kg)	DOSING		ALTERNATIVE DOSING ^a	
	Drug Concentration (reconstituted)	Volume (mL)	Drug Concentration (reconstituted)	Volume (mL)
5.5-6.6	11.0 mg/mL	0.13	22.0 mg/mL	Contact Medical Monitor
6.7-7.9	11.0 mg/mL	0.16	22.0 mg/mL	Contact Medical Monitor
8.0-9.5	11.0 mg/mL	0.19	22.0 mg/mL	Contact Medical Monitor
9.6-11.4	11.0 mg/mL	0.23	22.0 mg/mL	Contact Medical Monitor
11.5-13.9	11.0 mg/mL	0.27	22.0 mg/mL	Contact Medical Monitor
14.0-16.4	11.0 mg/mL	0.33	22.0 mg/mL	Contact Medical Monitor
16.5-19.9	11.0 mg/mL	0.39	22.0 mg/mL	Contact Medical Monitor
20.0-23.9	11.0 mg/mL	0.47	22.0 mg/mL	Contact Medical Monitor
24.0-28.9	22.0 mg/mL	0.29	11.0 mg/mL	0.57
29.0-34.9	22.0 mg/mL	0.35	11.0 mg/mL	0.69
35.0-41.9	22.0 mg/mL	0.41	11.0 mg/mL	0.83
42.0-50.9	22.0 mg/mL	0.50	11.0 mg/mL	0.50 + 0.50
51.0-60.5	22.0 mg/mL	0.60	11.0 mg/mL	0.60 + 0.61
60.6-73.4	22.0 mg/mL	0.73	11.0 mg/mL	0.73 + 0.73
73.5-87.7	22.0 mg/mL	0.88	11.0 mg/mL	0.88 + 0.88

^a To be used only when drug availability requires
kg = kilogram; mg = milligram; mL = milliliter

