The reason for administering the exact volume as per Table 1 (rather than calculating the exact dose) is as follows. At the conclusion of this 26-week trial, if eligible, subjects may choose to enter the extension trial, CT-301EXT, during which TransCon hGH will initially be administered by syringe and needle. When the auto-injector, a unique device developed specifically for the administration of TransCon hGH, becomes available, subjects will be switched from the administration of TransCon hGH by syringe and needle to the auto-injector.

With the auto-injector, TransCon hGH will be provided in single-use dual chamber cartridges (DCCs). Multiple DCC presentations will be available containing 20% incremental increases in dose to support increasing weight ranges. Thus, each DCC will contain a specific quantity of TransCon hGH to support a specific weight range consistent with Table 1. The intention within this trial is to mimic dose increments that will eventually be administered via the auto-injector in the CT-301EXT (extension) Trial.

Additionally, dosing based on volumes for weight ranges with 20% bracketing assures that all subjects will receive an average of 0.24 mg/kg/week over the course of the trial.

Please refer to the Investigator's Brochure for complete details on the composition and characteristics of TransCon hGH.

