9.6 Dose Adjustments

9.6.1 Dose Adjustment Parameters

The following parameters may be used by the investigator to adjust the TransCon hGH dose without Medical Monitor pre-approval.

At Visit 2, the TransCon hGH dose will be adjusted by the investigator based on weight (See [Section 9.3](#)).

Additionally, the goal for IGF-1 should be between 0 and + 2.0 SDS (unless a different target is identified in consultation with the Medical Monitor). Thus, if the IGF-1 SDS measured at Visit 2 (or the C_{max} Visit, as applicable) is < 0 SDS, and following confirmation of IGF-1 level as < 0 SDS by a second measurement collected 5 days post-dose (± 1 day) at an unscheduled visit, the dose may be increased by approximately 20% to the next higher weight bracket by the investigator (See [Section 9.3](#)).

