9.6.2 Stopping/Dose Reductions

The investigator (with Medical Monitor pre-approval) or Medical Monitor (and, if needed, with the ISC review) may stop or reduce the dose of study drug for an individual subject at any time during the trial in the presence of the following symptoms and laboratory abnormalities:

- Severe hGH-related AEs at any time during the trial (eg, peripheral edema, severe headache, intracranial hypertension or other adverse drug reaction and/or abnormal laboratory values)
- Pregnancy

Subjects who are sexually active must use an effective form of contraception

- IGF-1 > +2.0 SDS measured at Visit 2 (or the C_{max} Visit, as applicable) should be confirmed by a second measurement collected 5 days post-dose (±1 day) at an unscheduled visit. If the IGF-1 SDS is still elevated above +2.0, the TransCon hGH dose may be decreased by approximately 20% to the next lower weight bracket, unless a different target is identified in consultation with the Medical Monitor.

Any re-establishment of the original dose (0.24 mg hGH/kg/week) due to a subsequent sub-optimal IGF-1 response should receive prior approval by the Medical Monitor.

- Substantially reduced IGF-1 and growth response or evidence of a hypersensitivity to TransCon hGH
- Evidence of clinically significant pre-diabetes or diabetes (HbA1c > 6.2% measured at Visit 2 and an absolute increase of 0.5% from Screening HbA1c) should be confirmed by a second measurement at an unscheduled visit. If the repeat values are the same or higher, the TransCon hGH dose may be decreased by approximately 20% to the next lower weight bracket.* If appropriate follow-up monitoring shows progressively worsening glucose intolerance, additional TransCon hGH dose adjustments may be appropriate.

* If a subject had evidence of borderline glucose intolerance or diabetes prior to starting study drug (eg, fasting plasma glucose (FPG) 98 mg/dL and HbA1c 5.9%), treatment of hyperglycemia should occur prior to study drug treatment adjustment.

- Clinical evidence of benign intracranial hypertension (BIH) based on history and physical exam, including visual changes, headaches, nausea, vomiting, and/or papilledema on funduscopy should result in discontinuation of TransCon hGH treatment and clinical management

Reinstitution of TransCon hGH treatment, preferably at a lower dose, should receive prior approval by the Medical Monitor.

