- ¹⁸ Dose adjustments at visits are based on subject weight at visits. However, dose adjustments may occur between visits per protocol Section 9.6.

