8.8. OTHER ASSESSMENTS

Other safety assessments include weight, pubertal status, fundoscopy and bone age.

Weight and pubertal status are measured at screening and at Visits 1, 2 and 3. Summary tables will be produced for these assessments by visit.

Fundoscopy is measured at screening and the end of study. A listing will be presented for fundoscopy at each visit.

Bone age and delay in bone age are measured at screening. Listing will be provided for bone age and delay in bone age.

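### SAP 8.7 judges dose changes against a flat 0.24 mg/kg/week at an unnamed weight, so some one-bracket dose adjustments are tabulated as not changed

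*SAP*

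**What the plan says.** SAP 8.7 computes each dose in mg as volume times concentration. For three or more consecutive doses it then applies this test: "more than 15% difference between actual dose and expected dose (0.24mg/kg/week), it will be considered as a dose reduction/increase". Subjects are tabulated by visit as not changed, increased or decreased. The section does not say which weight turns mg into mg/kg, although by SAP 8.8 "Weight and pubertal status are measured at screening and at Visits 1, 2 and 3".

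The protocol does not assign 0.24 mg/kg to any individual child. Under Protocol 9.3 investigators must not calculate a weight-based dose but "follow the chart and administer the exact volume (based on weight) of the given concentration as indicated". Table 1 has 15 weight brackets. The figure 0.24 is what bracket dosing is expected to average: subjects "will receive an average of 0.24 mg/kg/week over the course of the trial".

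The individual adjustments for IGF-1 and HbA1c are defined as bracket steps. For a confirmed low IGF-1 SDS, Protocol 9.6.1 says "the dose may be increased by approximately 20% to the next higher weight bracket by the investigator". For a confirmed high IGF-1 SDS, Protocol 9.6.2 says "the TransCon hGH dose may be decreased by approximately 20% to the next lower weight bracket", and it gives the same step for a confirmed HbA1c rise. Footnote 18 to the SAP's Schedule of Events separates these from changes that follow weight: "Dose adjustments at visits are based on subject weight at visits. However, dose adjustments may occur between visits per protocol Section 9.6".

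**The concern.** The rule measures a bracket-based change against a reference that the protocol does not use for individual subjects. On-chart doses already sit up to 11% either side of 0.24, which uses most of the 15% margin. A decrease in a child near the light end of a bracket, or an increase in a child near the heavy end, starts on the wrong side of 0.24 and can end within the margin. That child is then tabulated as not changed.

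The unnamed weight is a second gap. Two programmers following SAP 8.7 could choose different weights and produce different tables.

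This is the SAP's only planned tabulation of dose changes in a trial whose primary objective is safety and tolerability. It will be read beside the IGF-1 SDS results, which themselves trigger adjustments.

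**Working it through.** **Inputs.** Table 1 concentrations, volumes and bracket limits (Protocol 9.3); entry weight 5.5 to 80 kg (Protocol 8.1.2); 15% limit and 0.24 mg/kg/week (SAP 8.7); one-bracket steps (Protocol 9.6). Amount in mg = concentration × volume, preferred dosing.

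**1. The protocol's own figure.** Protocol 9.3 states an average of 0.24 ± 0.02 mg/kg/week. With uniform weight in a bracket from a to b, mean mg/kg = mg × ln(b/a)/(b − a). For 29.0-34.9 kg: 7.70 × ln(34.9/29.0)/5.9 = 0.242. All 15 bracket means lie between 0.235 and 0.242, so 0.24 reproduces as an average.

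**2. On-chart range.** Lowest: 2.97/13.9 = 0.214 mg/kg (-11%). Highest: 6.38/24.0 = 0.266 mg/kg (+11%). At the weight that set the dose, no unadjusted child is flagged in any bracket.

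**3. One-bracket steps.** Decreases run from 9.02 to 7.70 mg (-14.6%) to 6.38 to 5.17 mg (-19.0%). Increases run from 7.70 to 9.02 mg (+17.1%) to 5.17 to 6.38 mg (+23.4%).

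**4. Examples that need no weight distribution.** The unflagged band is 0.85 × 0.24 = 0.204 to 1.15 × 0.24 = 0.276 mg/kg.
- 29.0 kg, 7.70 lowered to 6.38 mg: a 17% cut, but 6.38/29.0 = 0.220, only 8% below 0.24.
- 41.9 kg, 9.02 raised to 11.00 mg: a 22% rise, but 11.00/41.9 = 0.263, only 9% above 0.24.

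Both are tabulated as not changed.

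**5. Cut-points in one bracket (29.0-34.9 kg).** A decrease is missed below 6.38/0.204 = 31.3 kg, and an increase is missed above 9.02/0.276 = 32.7 kg. With uniform weights each is about 38% of the bracket: (31.27 − 29.0)/5.9 and (34.9 − 32.68)/5.9.

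**6. All 14 decreases and 14 increases.** Assumptions: dosing weight used, weights capped at 80 kg, all 28 moves weighted equally.

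| Weights within bracket (assumed) | Decreases missed | Increases missed | Pooled |
|---|---|---|---|
| Uniform | 36% | 28% | 32% |
| Clustered mid-bracket (symmetric triangular) | 27% | 17% | 22% |

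Under uniform weights the range by bracket is 23-42% for decreases below 73.5 kg and 20-38% for increases. The 73.5-80 kg bracket gives 80% for decreases, because 16.06/0.204 = 78.7 kg; without it the mean for decreases is 32%. Triangular weights skewed to the light or heavy end give 33% and 32% pooled.

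**7. Effect of the unnamed weight.** Same uniform, capped calculation, with the dividing weight above the weight that set the dose by an assumed amount.

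| Excess weight | Decreases missed | Increases missed | Unadjusted children flagged as reduced |
|---|---|---|---|
| 0% | 36% | 28% | 0% |
| 5% | 8% | 56% | 0.1% |
| 8% | 0% | 72% | about 6% |

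Example of a false flag at 8%: 2.97/(13.9 × 1.08) = 0.198 mg/kg, below 0.204.

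**8. Larger reductions.** The two-bracket reduction closest to 0.24 at the dosing weight is, for instance, 7.70 mg at 42.0 kg: 0.183 mg/kg, 23.6% below. Two-bracket reductions are therefore always flagged at that weight.

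**9. If expected dose meant the Table 1 amount.** With the 15% limit kept, all 14 increases and 12 of 14 reductions are detected. Still missed: 2.97 to 2.53 mg (-14.8%, 11.5-13.9 kg) and 9.02 to 7.70 mg (-14.6%, 35.0-41.9 kg).

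**The case against.** The strongest defence is that the table is meant to show departure from nominal exposure, not decisions made under Protocol 9.6. On that view, 6.38 mg at 29.0 kg is 0.220 mg/kg, inside the stated 0.24 ± 0.02, and leaving it unflagged is coherent. The 15% limit may also have been set to tolerate the bracket spread, and at the dosing weight it does produce no false flags. Every dose appears in listings, and no endpoint or model uses the category.

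The last point stands and limits the importance of the finding. The exposure reading is weak, because SAP 8.7 labels its categories as reduction, increase and not changed. Listings do not correct a summary that puts an adjusted child in the wrong row. Reading the reference as the Table 1 amount is not what the text prints, and it still leaves two reductions undetected.

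A reader might infer more than the documents support, in two ways:
- *That every Section 9.6 change is at risk.* It is not. Protocol 9.6.2 also allows stopping, and reductions not limited to one bracket; two-bracket reductions are always flagged at the dosing weight.
- *That the table can only undercount.* This holds at the dosing weight. With a higher weight, unadjusted children can be flagged as reduced, so the direction depends on a choice that SAP 8.7 leaves open.

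**Conclusion.** The rule is wrong as written and should be corrected. It places some real one-bracket adjustments in the not-changed row; the two examples at 29.0 and 41.9 kg show this without any distributional assumption. The share missed is about 22% to 32% of one-bracket moves, assuming the dosing weight is used and weights are clustered mid-bracket or uniform. The documents give neither a weight distribution nor the number of adjustments, so no count of affected subjects can be stated.

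The direction of error rests on the unnamed weight: misses without false flags at the dosing weight, but a mixture of missed increases and falsely flagged reductions if the weight used is 8% higher. The effect is confined to one descriptive exposure table.

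**What to change.** In SAP 8.7:

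1. Set the reference as the Table 1 amount for the subject's weight at the last dosing visit (Visit 1, then Visit 2), and name that weight.
2. Keep the three-consecutive-dose condition. Replace the 15% limit with a bracket comparison: match the administered amount to its Table 1 bracket and count one or more brackets away from the assigned bracket as increased or decreased. Use preferred dosing, or alternative dosing where Table 1 gives a volume. That is the case for the seven brackets from 24.0 kg up, where the two differ by at most 1.7% (6.27 against 6.38 mg).
3. Classify an amount that matches no bracket, or that lies below the lowest or above the highest, by whether it is lower or higher than the assigned amount.
4. Do not count moves that only follow weight. Show separately, and not as decreased, subjects who crossed a bracket at Visit 2 but stayed on the same amount.

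A related but separate point bears on item 4. The Protocol Synopsis, under Dose Adjustment Parameters, says "At Visit 2, the TransCon hGH dose may be adjusted by the investigator based on the TransCon hGH bracketed weight table", while the Synopsis under Treatment Regimens and Protocol 9.6.1 say that the dose will be adjusted by weight. The sponsor must reconcile these; no view is taken here on which is right.

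The cost is SAP wording, simple programming and one extra table row. Weight, volume, concentration and dose dates are already collected.

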8.8. OTHER ASSESSMENTS

Other safety assessments include weight, pubertal status, fundoscopy and bone age.

Weight and pubertal status are measured at screening and at Visits 1, 2 and 3. Summary tables will be produced for these assessments by visit.

Fundoscopy is measured at screening and the end of study. A listing will be presented for fundoscopy at each visit.

Bone age and delay in bone age are measured at screening. Listing will be provided for bone age and delay in bone age.

9. EFFICACY ANALYSES

9.1. ANNUALIZED HV

Annualized height velocity is calculated based on the rules stated in [Section 5.4](#). An ANCOVA will be used to analyze by visit annualized height velocity. The model will include baseline age, peak GH levels (log transformed) at diagnosis, delta mid-parental height SDS, prior GH dose level (log transformed), and duration (log transformed) as covariates, and gender as a factor.

Summary tables including data and listings will be presented for all height measured during the trial.

9.2. ΔHSDS

Height Standard Deviation Score (HSDS) is derived based on the rules stated in [Section 5.4](#). The by visit change from baseline of the HSDS will be analyzed by ANCOVA model including baseline age, peak GH (log transformed) at diagnosis, delta mid-parental height SDS, prior GH dose level (log transformed), and duration (log transformed) as covariates, and gender as a factor.

Summary tables and Figures will be provided for HSDS and change from baseline in HSDS at each time point. Listings will also be generated for all the HSDS information.

9.3. IGF-1 SDS AND IGFBP-3 SDS

A descriptive table including the frequency and percentages of subjects by each visit will be presented where:

- $0 \leq \text{IGF-1 SDS} \leq 2.0$
- $-2.0 \leq \text{IGF-1 SDS} \leq 2.0$
- $-1.0 \leq \text{IGF-1 SDS} \leq 2.0$
- $\text{IGF-1 SDS} > 2.0$
- $\text{IGF-1 SDS} > 3.0$

The by visit post baseline values and change from baseline in IGF-1 SDS and IGFBP-D SDS will be analyzed by ANCOVA model, including baseline age, peak GH (log transformed) at diagnosis, baseline (of the corresponding variable), prior GH dose level (log transformed), and duration (log transformed) as covariates, and gender as a factor.

The absolute values and change from baseline at each visit of the IGF-1, IGFBP-3, IGF-1 SDS and IGFBP-3 SDS will be also presented with descriptive statistics. Listings will be generated for these outcomes.

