8.2 Premature Subject Withdrawal

Early withdrawal occurs when an enrolled subject ceases participation in the trial, regardless of the circumstances, prior to the expected completion of the trial. Additionally, the investigator may discontinue the treatment of a subject at any time if considered to be in the subject's best interest. Unless informed consent is withdrawn, any subject who discontinues treatment should be encouraged to remain in the trial and attend all subsequent clinic visits. See [Section 7.3.1](#) for a list of stopping rules governing early termination of subjects from the trial.

In the case of premature discontinuation of a subject's participation in the trial (eg, withdrawal of informed consent), the investigator should schedule an Early Termination Visit to collect data, particularly AE follow-up data (if applicable), and to collect blood for laboratory evaluations. This visit should contain all assessments from Visit 3 (Week 26), and should be documented in the eCRF together with the reason(s) for trial discontinuation. In the case of treatment discontinuation for causes other than withdrawal of informed consent, subjects should be urged to remain in the trial and attend all subsequent trial visits. An Early Termination Visit is not required for subjects who remain in the trial after discontinuing study drug. However, if the subject is not willing to attend all subsequent trial visits, this should be considered a withdrawal from the trial and an Early Termination Visit should be scheduled.

Every effort should be made to observe subjects who have received at least 1 dose of study drug for the entire observation period, even if they discontinued trial treatment. The investigator should make every attempt to contact the subject/parent/legal guardian via phone to arrange the appropriate follow-up assessment(s) for such subjects.

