- *De novo* diagnosis of a slipped capital femoral epiphysis should result in a dose reduction or temporary discontinuation
- Identification of anti-hGH antibodies that are determined to be neutralizing

If treatment is discontinued, all subsequent visits and assessments should continue as planned. For additional details, refer to [Section 8.2](#).

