3.3.3. C_{max}/Pharmacodynamic Endpoints

- Expected C_{max} of hGH in subjects <3 years old
- Serum IGF-1 SDS at 1-2 days post-dose in subjects <3 years old
- Serum IGF-1 SDS at 5 days \pm 1 day post-dose in all subjects

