5.5. ANALYSIS POPULATION

The Screened Population includes all the subjects who are screened for this study and have any data captured in the EDC.

The Full Analysis Set includes all subjects who receive at least one dose of study drug during the trial and who have any follow-up data. The efficacy and safety analysis will be performed based on Full Analysis Set.

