8.4. IGF-1 SDS

A descriptive table including the number and percentages of subjects by visit will be presented where:

- IGF-1 SDS > 2.0
- IGF-1 SDS > 3.0

Listings of IGF-1 and IGF-1 SDS for subjects with abnormally high IGF-1 SDS will be generated.

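### The SAP tabulates IGF-1 by visit without checking time since the last injection, so off-drug and off-interval samples count as Visit 3, 5-day post-dose results

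*SAP*

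**What the plan says.** **Endpoints.** SAP 3.3.3 and 10 define the pharmacodynamic endpoint as serum IGF-1 SDS at 5 days ±1 "day post-dose in all subjects", with a 1-2 day post-dose endpoint for children under 3. SAP 3.3.2 places the proportion with IGF-1 SDS of 0 to +2.0 at 26 weeks of weekly TransCon hGH treatment.

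**Who is sampled.** Protocol 8.2 says that, unless consent is withdrawn, "any subject who discontinues treatment should be encouraged to remain in the trial and attend all subsequent clinic visits". Protocol 9.6.2 adds: "If treatment is discontinued, all subsequent visits and assessments should continue as planned". Visit 3 includes an IGF-1 sample, and an Early Termination Visit repeats the Visit 3 procedures.

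**Who is analysed.** Under SAP 5.5 the Full Analysis Set "includes all subjects who receive at least one dose of study drug during the trial" and has any follow-up data. The same section states: "The efficacy and safety analysis will be performed based on Full Analysis Set".

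**Which visit a sample belongs to.** SAP 5.3 repeats the 5 ±1 day timing and the permitted study days for the scheduled visits. Unscheduled and Early Termination visits are mapped to the scheduled visit with the closest target day. In SAP Table 2 the Visit 3 target is Day 183 and the range is Day 138 to end of study.

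**What is tabulated.** SAP 8.4, for IGF-1 SDS above 2.0 and above 3.0: "A descriptive table including the number and percentages of subjects by visit will be presented where". SAP 9.3, for the target ranges as well: "A descriptive table including the frequency and percentages of subjects by each visit will be presented where". SAP 9.3 also fits by-visit ANCOVA models to IGF-1 SDS and IGFBP-3 SDS.

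**The concern.** Two of the IGF-1 endpoints are defined by time since an injection, and the efficacy endpoint presumes continuing weekly treatment. The SAP states that timing as schedule and as endpoint definition, but gives no rule that applies it to the data. Nothing in SAP 5.3, 8.4, 9.3 or 10 excludes, flags or separates a sample drawn after study drug was stopped or outside 4-6 days post-dose. SAP 6.2 provides only a listing of major deviations. Followed as written, the plan reports such a sample as a Visit 3 value.

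Safety is the primary objective, and the incidence of high IGF-1 SDS is one of its endpoints. If IGF-1 falls once the drug is stopped, off-drug samples make the Visit 3 high-IGF-1 percentages look better than they are on treatment. The target-range percentage then describes a mixture of treated and untreated children under an on-treatment label.

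**Working it through.** **1. The plan's own visit days reproduce.** With weekly dosing from Day 1, dose *k* falls on Day 1 + 7(*k* − 1). Doses 25, 26 and 27 fall on Days 169, 176 and 183. Adding 4 to 6 days gives Days 173-175, 180-182 and 187-189, exactly the Visit 3 days in Protocol 10.2.2 and SAP 5.3. (The only computed design figure, at least 95% probability of seeing an AE, also reproduces: 1 − 0.98^150 = 0.952 and 1 − 0.99^300 = 0.951. It does not bear on IGF-1.)

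**2. What the analysis rules accept.**
- Last dose was dose 13 (Day 85), child attends on Days 180-182: the sample is 95-97 days post-dose and is counted at Visit 3.
- Early Termination on any day from Day 138: mapped to Visit 3 whatever the interval since the last dose. The schedule's shared Visit 3/ET column carries the 5 ±1 day timing, but a child already off drug cannot meet it.
- Dose 26 missed and the visit not moved: Days 180-182 are 11-13 days after dose 25, still inside the window.
- The mapping targets do not track dosing. Day 183 is 183 − 176 = 7 days after dose 26, and Day 92 is 92 − 85 = 7 days after dose 13. Both lie outside 4-6 days.

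**3. How far drug exposure falls.** Protocol 5.3 gives a terminal hGH half-life of 21.8 to 25.4 hours after a single dose in healthy subjects. One further week is 168 h, or 168/25.4 = 6.6 to 168/21.8 = 7.7 half-lives. That leaves 2^(−6.6) ≈ 1.0% to 2^(−7.7) ≈ 0.5% of the 5-day hGH level. This is hGH; the documents give no decay rate for IGF-1.

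**4. Size of the shift.** Let *d* be the share of summarised children whose Visit 3 sample is off drug. Shift = *d* × (rate off drug − reference rate). Both rates lie between 0 and 1, so the shift cannot exceed *d*. The documents give neither *d* nor the rates; all values below are assumptions.

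| Scenario (shift in percentage points) | d = 2% | d = 5% | d = 10% |
|---|---|---|---|
| In range: 50% on drug, 0% off drug | −1.0 | −2.5 | −5.0 |
| In range: 70% on drug, 0% off drug | −1.4 | −3.5 | −7.0 |
| In range: stoppers all > +2.0 on drug, 60% fall into range off drug | +1.2 | +3.0 | +6.0 |
| > +2.0: 10% on drug, 0% off drug | −0.2 | −0.5 | −1.0 |
| > +2.0: stoppers all > +2.0 on drug, 0% off drug | −2 | −5 | −10 |

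The reference is the on-drug children in rows 1, 2 and 4, and the same stoppers had they stayed on drug in rows 3 and 5. At N = 150, *d* of 2%, 5% and 10% is 3, 7.5 and 15 children.

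**5. Scale.** The 95% confidence half-width at N = 150 is 1.96 × √(p(1 − p)/150): 8.0 points at p = 50% and 4.8 points at p = 10%. Most of the shifts above are smaller than that, but they are systematic and do not shrink with sample size.

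**The case against.** The strongest defence is that retaining off-drug children is deliberate and that summarising every treated child is a legitimate treatment-policy description in a single-arm, largely descriptive trial. That stands as a reason to keep the all-subjects table. It does not rescue the labelling: the SAP does not claim a treatment-policy reading, and a sample taken months after the last dose cannot represent a 5-day post-dose endpoint.

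A table restricted to on-drug samples has its own weakness, because it describes only children who stayed on treatment. Suppose 10% of on-drug children exceed +2.0, and 5% of all children stop, every one of whom would have stayed above +2.0. The current table shows 0.95 × 10% = 9.5%, the restricted table 10.0%, and the value with everyone on drug is 9.5% + 5% = 14.5%. Neither table alone is enough.

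Several stronger readings might be inferred, and the documents do not support them:
- *All records are assigned by study day alone.* That mapping is written only for unscheduled and Early Termination visits. Scheduled visits carry the post-dose timing; what is missing is its enforcement in the analysis.
- *A missed last injection is as serious as stopping.* Protocol 10.2 ties Visit 3 to the 25th, 26th or 27th dose with ±1 week, so the visit can often be moved. The case matters only when it is not.
- *Children with high IGF-1 are taken off drug and reappear as normal.* The lead sentence of Protocol 9.6.2 says the investigator or Medical Monitor "may stop or reduce the dose of study drug for an individual subject at any time during the trial", but its bullet for IGF-1 above +2.0 describes a dose decrease after confirmation. Such a child remains on drug and can be validly sampled at Visit 3.
- *Over-exposure is hidden.* A high Visit 2 value is still tabulated at Visit 2, and SAP 8.4 requires listings of abnormally high values.
- *The in-range percentage is necessarily lowered.* Children above +2.0 on drug may fall into range.
- *The half-life fixes the IGF-1 decline.* It describes hGH only.
- *Height velocity and ΔHSDS need the same restriction.* No error in those analyses has been identified on this ground.

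**Conclusion.** The mismatch is real: the endpoints are tied to dosing, and the by-visit analysis is not. Off-drug and off-interval samples will be reported as Visit 3 results because no rule prevents it. The clearest cases are permanent discontinuation and Early Termination draws.

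Assuming IGF-1 falls off drug, the Visit 3 percentages above +2.0 and +3.0 are biased downward, and the 0 to +2.0 percentage can move in either direction. The limit is the share of such samples: none if nobody stops or is sampled off interval, and at most 2 to 10 points at an assumed 2% to 10%, reached only if every such child changes category. A draw earlier than 4 days post-dose is also off interval; the documents do not give the IGF-1 profile needed to say which way it would act. The effect is probably modest, but it touches a primary-objective safety table and can be removed before database lock.

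**What to change.** In SAP 8.4, 9.3 and 10.2:

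1. Derive days since the last TransCon hGH injection for every IGF-1 and IGFBP-3 sample, from the diary and eCRF dates.
2. Base the 5-day post-dose summaries at Visits 2 and 3 on samples drawn 4-6 days after an actual injection, and the C_max Visit summary on samples drawn at 1-2 days.
3. Limit the denominator to children with such a sample. Under the default in SAP 5 (all subjects in the population), excluded children would otherwise count as not in range.
4. Show off-interval and post-discontinuation samples in a separate row, with the reason for stopping.
5. Keep the all-subjects by-visit table alongside.

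The cost is SAP wording and one derived variable. Protocol 9.8 and 11.8 already collect injection dates, and SAP Table 3 already uses the last treatment date. No sample-size figure changes. The downsides are a slightly smaller denominator and a restricted table that describes only children still on treatment, which is why both tables are needed.
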